27 JUNE 2017

Title Page

Study Title: A Pilot Feasibility Study Comparing a Novel Phototherapy Kiosk to Supplementation to Promote Vitamin D Sufficiency

Name of Product Tested: Solius, Photobiologic therapy kiosk

Indication Studied: Maintenance or repletion of serum 25(OH)D status

Study Description: This pilot feasibility study was designed to provide validation of the isolation of narrow spectrum ultraviolet B (UVB) rays delivered in a standing kiosk. A measured dose was administered under conditions of full body exposure every other week for 10 weeks. The stimulation of cutaneous vitamin D and subsequent 25(OH)D production from phototherapy was compared to the effect of an IOM determined RDA dose of 600 IU vitamin D3 supplement daily for 10 weeks. The primary outcome was serum 25(OH)D level.

Sponsor: BeneSol, Inc. dba SOLIUS

Protocol: Non-inferiority, feasibility, randomized, controlled trial with Institutional Review Board approval as a minimal risk human use protocol.

Phase of Development: Premarket

Study Initiation Date: 21 August 2017

Study Completion Date: 11 March 2019

Name of principal or coordinating investigator: [name], RN. Madigan Army Medical Center

DCP Statement: This study was performed in compliance with ICH Good Clinical Practice (GCP) including the archiving of essential documents.

1 List of Abbreviations & Definition of Terms

AD	Active duty
BIA	Bioelectrical impedance analysis
BMI	Body mass index
BMR	Basal metabolic rate
CAP	College of American Pathologists
CG	Comparison group
DXA	Dual energy xray absorptiometry
FST	Fitzpatrick skin type
IQR	Interquartile range
IRB	Institutional Review Board
JBLM	Joint Base Lewis-McChord
MAMC	Madigan Army Medical Center
MCAR	Missing completely at random
Mdn(mdn)	Median
Nm	Nanometer
Ng:	Nanogram
SM	Service member
SPK	Standing phototherapy kiosk
TG	Treatment group

2 Ethics and Regulatory Approval

2.1 Institutional Review Board (IRB) or Independent Ethics Committee (IEC) Approval

The study protocol and all its amendments were reviewed and approved by the IRB as detailed in table one below.

IRB Name	Regional Health Command – Pacific Institutional Review Board
Principal Investigator	[name], RN, MAMC
Date of approval of the final protocol	27 June 2017
Date of approval of amendment 1	5 October 2017
Date of approval of amendment 2	9 March 2018
Date of approval of amendment 3	11 May 2018

The study was performed in compliance with FDA 21 CFR 812. Since the product under investigation is low risk, IRB approval is sufficient.

2.2 Ethical Conduct of the Study

The study was performed in accordance with the current version of the declaration of Helsinki (52nd WMA General Assembly, Edinburgh, Scotland, October 2000). The trial was conducted in agreement with the International Conference on Harmonization (ICH) guidelines on Good Clinical Practice (GCP).

2.3 Patient Information and Consent

All patients provided written informed consent to participate in the study prior to being screened. The patient was given a copy of the signed consent form for their personal records. The original copy of the informed consent is kept in document control along with this test report. A sample of the consent form can be found along with the IRB-approved study protocol.

3 Investigators and Study Administrative Structure

The table below shows the principal study personnel involved in the study.

Title	Name and Affiliation
Principal Investigator	[name], RN, FAAN. MAMC
Sponsor	BeneSol, Inc. dba SOLIUS
Project Manager	[name], MS, RD, LD. MAMC
Clinical Research Associate(s)	[name], BSN, RN. MAMC
Biostatistician	[name], MA. (Contractor)

4 Introduction

Low vitamin D status is common in individuals who regularly perform extreme physical exertion, particularly in combination with periods of psychological stress, inadequate nutrition, and sleep disruption.¹ This places military personnel in a high risk category with significant negative consequences to musculoskeletal, immune, and mental health, and thus, resilience. The large scope of this problem demands a multi-phased approach beginning with a self-care, easy access, safe biomedical device intended to stimulate cutaneous production of vitamin D. The pilot, or demonstration phase, involved installment of a standing phototherapy kiosk in an outpatient setting where we enrolled Active Duty (AD) and retired Service Members (SM), adult beneficiaries, and DA civilians to test the acceptability and feasibility of this health promotion concept. We anticipated that the phototherapy kiosk would be an inexpensive, convenient, and effective way to maintain or raise 25(OH)D levels to sustain Warfighter and beneficiary resilience.

Endogenous production of vitamin D comes from sun exposure, however concerns of skin cancer and heat injuries limits recommendations for even a safe level of exposure. The only alternative has been consumption of vitamin D supplements, yet there is a paucity of evidence for how often, how much, and for how long one should consume supplements. Unlike endogenous vitamin D, research shows that supplements do not bind completely to vitamin D binding protein and are not regulated in the body to prevent overdose.³²⁻³⁵ Fat malabsorption conditions (cystic fibrosis, Crohn's disease, celiac, liver disease, etc.) can reduce the ability to absorb fat soluble vitamin D supplements yet endogenous vitamin D production from UVB light is uninhibited.^{2,36-40} UVB radiation with a wavelength of 290-320 nm penetrates the exposed skin and converts cutaneous 7-dehydrocholesterol to pre-vitamin D3, which in turn becomes vitamin D3. Maximal immune system response occurs at a peak of 300 nm and vitamin D3 production at a peak of 298 nm.³ Sunlight exposure provides 80-100% of the body's vitamin D requirements. Factors that influence UVB exposure and vitamin D synthesis include season, time of day, length of day, cloud cover, smog, skin melanin content, and sunscreen. However, a simple "prescription" for midday sun exposure under a cloudless sky with 90% skin exposure and no sunscreen in a non-urban, minimally polluted environment is a challenge for almost every American, and even more so for Service Members.

The current standard of care is 600 IU oral vitamin D daily, which is the RDA established by the Institute of Medicine (IOM) who identified clinically significant levels of circulating 25(OH)D to be 20 ng/mL. The RDA for vitamin D represents a daily intake sufficient to maintain bone health and normal calcium

metabolism in 97.5% of the population.²⁰ While debate surrounds a sufficient range for 25(OH)D, there does seem to be a general acceptance that the optimum range is between 30 – 60 ng/mL.⁵⁻⁷ The human body uses sunlight as the primary source of vitamin D and produces large quantities efficiently with limited UVB exposure.¹²⁻¹⁵ Therefore, a rational way to determine the optimum vitamin D range is by studying natural cutaneous vitamin D synthesis. It has been demonstrated that a single session of full body exposure to solar radiation can produce a time-released equivalent of approximately 10,000 IU of oral vitamin D.¹⁶ A safe upper limit for vitamin D is related to oral intake only. Cutaneous vitamin D production is automatically regulated by a photochemical reaction and pigmentation, preventing toxicity.¹⁷⁻¹⁹ Consequently, hypervitaminosis D is not possible when the only vitamin D source is skin production following exposure to UVB light. For all these reasons, an innovative alternative to address low vitamin D status in adults, Warfighters included, is needed.

5 Study Objectives

The specific aims for this project were:

1. Determine acceptability and feasibility of a standing phototherapy kiosk designed as a self-care intervention for AD and retired service members, beneficiaries, and DA civilians;
2. Demonstrate that narrow spectrum UVB delivered by the SPK is at least equivalent to D3 oral intake to raise or maintain serum 25(OH)D levels over a 10-week intervention period;
3. Examine the relationship of demographic variables, including gender, age, body mass index, body fat, ethnicity, and sun exposure to serum 25(OH)D levels in both groups.

6 Investigational Plan

6.1 Overall Study Design and Plan

This non-inferiority study used a prospective, longitudinal, randomized design with repeated measures to address vitamin D sufficiency in AD, retiree, beneficiary, and DA civilian populations. It is important and necessary to conduct this study with adult humans, military personnel in particular, to determine acceptability and feasibility of this phototherapy kiosk as an addition to existing Warfighter resources to promote health and resilience. Following Madigan Army Medical Center (MAMC) Institutional Review Board Human Subjects and Ethics approval, the SPK will be installed in a location approved by the Radiation Safety Officer, the study team will be hired, and recruitment will begin for an anticipated 12-month project period. Approximately 120 volunteers will be approached from MAMC and Joint Base Lewis-McChord (JBLM), a large joint base in the Pacific Northwest, where over 25,000 Soldiers and Airmen train every day and regional beneficiaries' number ~98,000. Recruiting efforts will attempt to capture a representative sample of the population including both genders, diverse ethnicities, and a range of age (18-70 years) and body mass index (BMI), who have no contraindication for UVB exposure or oral vitamin D supplementation. In addition to walk-in volunteers, the research team will attend the JBLM Newcomer's Orientation. Using a computer-generated block design, volunteers will be randomized to one of two groups by the research pharmacist; 1) oral vitamin D supplementation, or 2) standing phototherapy kiosk with UVB exposure, for a 10-week period.

Comparison Group (CG) – Supplement

A MAMC research pharmacist will dispense a 70-day supply of the vitamin D3 600 IU oral supplement to subjects assigned to this group. The Project Director will work with the pharmacist to coordinate pick-up of supplement bottles for subjects or optimal in-person dispensing times.

Treatment Group (TG) – Phototherapy

The Project Director provides oversight for the phototherapy treatment. The kiosk will deliver the UVB dose under supervised conditions over a 1 – 10 minute interval based on the Fitzpatrick skin type with the subject wearing minimal or no clothing, preferably no more than a bathing suit, and protective eye-wear. The experience in the SPK was designed to be comfortable and user-friendly.

All eligible adult volunteers will be enrolled regardless of their baseline 25(OH)D level as it is important in this non-inferiority study to show there is no potential for harm from phototherapy, even if the baseline 25(OH)D level is above 30 ng/mL. If the goal is to develop a self-care kiosk, individuals will not have the ability to check their serum vitamin D status prior to use. We also want to learn the trajectory of vitamin D absorption and availability over a 3-4-month period in order to make evidence-based therapeutic recommendations. It is not possible to blind the subjects or research team to the group assignment given the two comparators.

Serum levels of 25(OH)D, calcium, and parathyroid hormone are drawn at baseline (T0), immediately following the intervention at 10 weeks (T6); at 14 weeks (T8), 25(OH)D is drawn to document sustainment of treatment effect. Remuneration in the form of \$20 Amazon gift cards is provided to all volunteers after the baseline and final scheduled blood draw (as allowed by DoD Instruction 3216.02 Dated November 8, 2011).

A survey shall be completed at T1 and reviewed with participants again at the 10-week visit to capture relevant demographic, medical history, sun exposure, travel, daily activities, and dietary data. Active duty SMs shall report the number of days on profile (activity restriction) for the previous three months, at T1 and T6. A Device Usability Scale will be administered to the kiosk group participants upon protocol completion to address acceptability and feasibility of the treatment. With the assistance of a biostatistician, we will analyze data using repeated measures analysis of variance adjusting for significant covariates such as 25(OH)D level at baseline. Logistic regression analyses are used to predict outcomes and explain the interrelationships among variables, i.e. age, gender, BMI, body fat, ethnicity, and sun exposure relationship to 25(OH)D serum levels.

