6.2 Discussion of the Study Design, Including the Choice of Control Groups

The objective of this non-inferiority study is to demonstrate the ability of the phototherapy kiosk to safely administer UVB radiation to participants with sufficient or insufficient levels of 25(OH)D and achieve comparable levels of serum 25(OH)D in a similar population of adults randomized to receive the RDA of 600 IU vitamin D oral supplementation once daily. As an experimental device, it is important to evaluate its equivalence to standard of care in the maintenance of sufficient levels of vitamin D in adults with all skin types between 18 and 69 years of age. In this study the supplement group (CG) was used as an active control.

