6.3.3 Removal of Patients from Therapy or Assessment

Participants enrolled in the study are free to withdraw at any time without repercussions; the study team requested to be informed in writing of their decision to withdraw.

Volunteers are reminded that the Principal Investigator of the research study may terminate their participation in the research study at any time if she determined this to be in their best interest, if they are unable to comply with the procedures required, or if they no longer meet eligibility criteria.

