6.4 Treatments

6.4.1 Treatments Administered

Comparison Group - Supplement

Volunteers assigned to this group are provided with a 10-week supply (70 pills) of a vitamin D3 supplement. Consented participants are instructed to take one 600 IU pill by mouth each day for ten weeks. They are instructed to take this with a meal. This dose is the RDA for adults between 18 and 69 years old according to the Institute of Medicine Committee to Review Dietary Reference Intakes for Vitamin D and Calcium.²⁰

Treatment Group - Phototherapy

Volunteers assigned to this group are administered phototherapy treatments once every other week, for 10 weeks. The treatment usually lasts no more than 10 minutes and is based on the Fitzpatrick skin type classification tool¹⁹ which is self-assessed via the computer touch screen in the kiosk.

Table 1. Study Summary

Phase	Initial (T)	Time 1 (T+1wk)	Time 2 (T+3wk) Time 3 (T+5wk) Time 4 (T+7wk) Time 5 (T+9wk) Time 6 (T+11wk)	Time 7 (T+15wk)
Screening	X			
Informed Consent	X			
Submit Blood Tests	X		X (Time 6)	X
Randomization	X			
Demographics and Surveys		X	X (Time 6)	
Inbody		X		
Treatment -Phototherapy (every other week x6)		X	X (Time 6 = Final Exposure)	
Device Usability Scale - Phototherapy			X (Time 6)	
Treatment -Vit D Supplement (daily for 10 weeks)		X	X	

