6.4.4 Selection of Doses in the Study

Comparison Group - Oral Supplement Dosing

For this non-inferiority study, the logical choice for a comparison arm was the Recommended Daily Allowance (RDA) of 600 IU vitamin D for adults in the age range of 18-70 years old. The RDA was established by the Institute of Medicine (IOM) who identified clinically significant levels of circulating 25(OH)D (20 ng/mL) and then estimated the amount of dietary vitamin D required to reach this circulating level with minimal sunlight exposure. The RDA for vitamin D represents a daily intake sufficient to maintain bone health and normal calcium metabolism in 97.5% the population.²⁰

Treatment Group - Phototherapy Dosing

All patients shall be dosed at 0.6 MED at a distance of 12" from the light source for all treatments. This is consistent with dosing demonstrated to be effective at raising serum 25(OH)D without the risk of adverse events.^{26, 27} Treatments shall occur on a 14-day interval (+/- 24 hours), for a total delivery of 6 doses.

To obtain dose, each participant will self-assess their skin type according to the Fitzpatrick skin typing scale using software inside the kiosk. The kiosk will determine the dose per patient, based on their answers. Erythema response to the previous treatment dose is self-assessed. In the event erythema is self-reported via the kiosk, the participant's dose is reduced by the system for subsequent treatments.

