6.4.8 Adherence

Comparison Group

Participants agree to oral administration of 600 IU vitamin D once per day. Participants must agree to abstain from ingesting oral vitamin D supplements. Participants must also have blood drawn at baseline, day 70, and at day 100.

Treatment Group

Participants must be exposed once every other week (14 days +/- 24 hours). Participants must agree to abstain from ingesting oral vitamin D supplements. Participants must also have blood drawn at baseline, day 70, and at day 100.

In this pilot feasibility study, one aim is to evaluate acceptability and adherence.

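### Usability is rated once, at Time 6, so leavers give no rating, and no skin report is described for any kiosk participant's last exposure

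*Combined protocol and SAP*

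**What the plan says.** **Usability.** Aim 1 (section 5) is acceptability and feasibility, and section 6.4.8 adds: "In this pilot feasibility study, one aim is to evaluate acceptability and adherence". The one rating instrument named is the 12-item Device Usability Scale. Section 6.1 gives its timing: "A Device Usability Scale will be administered to the kiosk group participants upon protocol completion to address acceptability and feasibility of the treatment". Sections 6.5.1 and 6.5.3 likewise tie it to completing the study, and Table 1 (section 6.4.1) marks it at Time 6 only.

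**Leaving the study.** For voluntary withdrawal, section 6.3.3 says that "the study team requested to be informed in writing of their decision to withdraw". It also says that the principal investigator "may terminate their participation in the research study at any time", and gives three grounds: the participant's best interest, inability to comply, or loss of eligibility. It describes no rating, no skin check and no recording of the reason. Section 6.5.1 does commit the team to counting completion and attrition by arm.

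**Skin response.** Section 6.2 gives the objective as "to demonstrate the ability of the phototherapy kiosk to safely administer UVB radiation". The capture described is in section 6.4.4: "Erythema response to the previous treatment dose is self-assessed". If erythema is reported through the kiosk, the "dose is reduced by the system for subsequent treatments". Six doses are given 14 days apart, and Table 1 places the last at Time 6 ("X (Time 6 = Final Exposure"). The only later contact in Table 1, Time 7, lists blood tests alone.

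**The concern.** Both gaps fall after a kiosk participant's last session, planned or actual.

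A scale given only to people who reach the end cannot describe those who stopped, and for a self-care device those who stopped are part of the acceptability question. Attrition counts show how many left. They do not show whether the kiosk, the schedule or something unrelated was the cause.

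The erythema question looks backwards, so it needs a later kiosk session to be asked. The last exposure has no later session. A statement about how many exposed participants had any skin reaction would then rest on an incomplete record. The record is thinnest for people who stopped early, who may have no report at all.

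**Working it through.** **Inputs.** Required sample 60, dropout 30%, enrolment 78 minimum and 120 requested (section 6.6.2). Six exposures 14 days apart (section 6.4.4). The allocation ratio is not stated, so 1:1 allocation and equal dropout by arm are assumed.

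**The plan's own figure.** 60 × 1.30 = 78, which matches the stated minimum. Whether that is the best way to allow for dropout is a separate matter.

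**Kiosk arm.** 78 / 2 = 39 and 120 / 2 = 60.

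**Participants without a usability rating.** Leavers: 0.30 × 39 = 11.7, about 12 (27 completers); 0.30 × 60 = 18 (42 completers). How many are unrated depends on when they leave:

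| Case | Enrolment 78 | Enrolment 120 |
|---|---|---|
| All leavers exposed, all gone before Time 6 | 12/39 = 31% | 18/60 = 30% |
| Half of leavers never exposed, counted separately | 6/33 = 18% | 9/51 = 18% |
| Half leave after Time 6, already rated | 6/39 = 15% | 9/60 = 15% |

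The first row is the upper end at the planned dropout.

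**Exposures without a described skin report.** Someone with k exposures (k at least 1) has k − 1 later kiosk sessions, so one exposure is always unreported and the unreported share is 1/k. For a completer this is 1/6 = 16.7%, with five reports. For someone who leaves after one exposure it is 1/1, with no report.

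Across the arm at full adherence: 39 / (39 × 6) = 39/234 = 16.7%, and 60/360 = 16.7%.

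At 30% dropout, with all leavers stopping after k exposures, the share is (number exposed) / (completers × 6 + leavers × k):

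| k | 39 in arm | 60 in arm |
|---|---|---|
| 1 | 39/174 = 22.4% | 60/270 = 22.2% |
| 3 | 39/198 = 19.7% | 60/306 = 19.6% |
| 5 | 39/222 = 17.6% | 60/342 = 17.5% |

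**Could anything else described fill the gap?** The usability scale asks about cleanliness, ease and comfort, and is given at the same visit as exposure six. The survey review at Time 6 covers history, sun exposure and diet. Delivery is supervised (section 6.1), so staff might see an immediate reaction, but no recording of it is described.

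**Recall if completers are asked at the final blood draw.** Table 1: week 15 − week 11 = 4 weeks = 28 days. Section 6.4.8: day 100 − day 70 = 30 days. For earlier exposures it is 14 days.

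**The case against.** **Argument from silence.** Section 2.3 refers to an IRB-approved study protocol kept with a test report, and skin-reaction capture is the kind of detail that a separate form would hold. This stands as a limit: the finding is that capture is not described here, not that it was not collected.

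**Completers are well covered.** A reader might infer that the erythema status of every completer is simply unknown. The documents do not support that. Section 6.4.4 sets one skin-type-adjusted dose level for all treatments, reduced only after reported erythema. As described, exposure six is no stronger than the five already reported on. For completers the loss is small, and the weight of the point falls on early leavers.

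**Usability might look flattering.** A reader might infer that the finisher-only result is biased upwards. Dissatisfied people may leave more often, but nothing in the documents shows it. Nor would best- and worst-case limits on a mean item score settle it. The plan names no mean score (section 6.6.1 uses medians with interquartile ranges, and counts), and such limits follow from the missing share on any 1-to-5 scale.

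**Reasons for leaving are partly available.** Investigator removals have three stated grounds, and a written withdrawal notice could carry a reason. That is fair, but recording the reason is not described for either route.

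**The 30% may be pessimistic.** The text of section 6.6.2 treats it as worse than expected, while its table enters it as the estimate. The counts above scale with it.

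**A single rating at the end of treatment is a common choice.** True, and acceptable if the result is labelled for what it covers.

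**Conclusion.** The point holds, at modest priority. Followed as written, the plan gives a usability result for finishers only, with up to about 12 of 39 or 18 of 60 kiosk participants unrated. It also leaves one exposure per exposed participant without a described skin report: 16.7% of exposures at full adherence, and at most about 22% at 30% dropout. The 22% needs every leaver to stop after exactly one exposure. These figures rest on 1:1 allocation, equal dropout by arm and the 30% allowance, and the rating counts also assume that all leavers were exposed and left before Time 6.

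The documents do not establish a direction of bias, and they do not show that skin reactions after the last exposure went uncollected. Leavers are not ignored altogether, because adherence is an aim and attrition is counted by arm. The serum 25(OH)D primary endpoint is untouched.

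**What to change.** 1. **Usability.** At withdrawal or removal, offer the existing 12-item scale to anyone exposed at least once, and record the reason for leaving. Report the numbers assigned, exposed and rated. Where leavers' ratings are missing, label the result as describing finishers only.
2. **Skin response.** Ask the existing erythema question about the last exposure at withdrawal. For completers, have the study team ask it briefly around the final scheduled blood draw, since no kiosk session or study-team contact is described there. That draw is Time 7 in Table 1 but T8 in section 6.1, and the labels should be reconciled. Report the proportion of exposed participants with any reported erythema with an exact 95% CI, and the number of exposures with no report. For scale: with a complete record and no events, the upper limit 1 − 0.025^(1/n) is 9.0% for n = 39 and 6.0% for n = 60.
3. **If a separate safety form already covers the last exposure,** cite it in place of item 2's new question.

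The cost is a reused form, a reused question and a brief extra contact, with no new clinic visit. The downsides are slight respondent burden, incomplete response from leavers, and 28 to 30 days' recall for exposure six. The title page gives a completion date of 11 March 2019. If collection has closed, the reporting and labelling steps can still be done. No dose or clinical rule is proposed.

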6.5 Efficacy and Safety Variables

6.5.1 Efficacy and Safety Measurements Assessed

To determine that phototherapy is at least equivalent to D3 oral intake to raise or maintain serum 25(OH)D levels over a 10-week intervention period baseline 25(OH)D levels are obtained.

Blood draws will occur upon enrollment with two follow-up measurements, one at 10 weeks and a final level 4 weeks after completing the protocol to evaluate sustainment of the post-treatment level. Serum concentration of 25(OH)D is the best indicator of vitamin D status as it represents cutaneous production and consumption of food and supplements. Serum 25(OH)D has a circulating half-life of 15 days.²⁸ Serum 25(OH)D levels do not indicate the amount of vitamin D stored in body tissues.¹⁰ All blood levels will be obtained by experienced phlebotomists in the hospital central laboratory. There will be no standardization of time of day for the blood draw. An Endocrine consultant will review all abnormal lab values [(25OH)D, PTH, Calcium] and recommended follow-up with the Primary Care Manager, if necessary.

To determine acceptability and feasibility of the standing phototherapy kiosk, a Device Usability Scale will be administered to the Kiosk Group upon completion of the study. This 12-item Likert-type scale was adapted from the Digital Equipment Corporation "System Usability Scale" (1986). Questions assessed cleanliness, ease of use, and comfort of the kiosk with a Likert-type scale where 1= Strongly disagree to 5 = Strongly agree.

The research team will meticulously track the number of potential participants screened, the number of enrolled subjects, completion of all study timepoints, and attrition from each arm.

To examine the relationship of demographic variables, including gender, age, body mass index, body fat, ethnicity, and sun exposure to serum 25(OH)D levels in both groups, several other measurements will be obtained including the following:

1. Body height (Ht) – Vertical height is measured at baseline using a Harpenden Stadiometer and recorded to the nearest 0.1 cm. The stadiometer is composed of a rigid vertical backboard with an attached rigid horizontal headboard which moves up and down the backboard. Final height was the average of two measurements taken by trained study staff.

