6.5.3 Primary Efficacy Variable(s)

Serum 25(OH)D level is the primary endpoint used to establish whether the treatment in the phototherapy kiosk group is equivalent to the oral vitamin D3 supplementation currently prescribed as the standard of care. It is expected that the serum 25(OH)D levels in both groups will rise over time and that the serum 25(OH)D levels will be equal to, or not less than, that of the oral supplementation group.

A Device Usability Scale will be administered to the Kiosk Group to assess acceptability and feasibility. This 12-item Likert-type scale was adapted from the Digital Equipment Corporation

“System Usability Scale” (1986) and it will be administered to the Kiosk Group upon completion of the study.

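### Non-inferiority on serum 25(OH)D is claimed with no margin, alpha or confidence-limit rule, so the planned repeated-measures ANOVA has no stated route to the Aim 2 conclusion

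*Combined protocol and SAP*

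**What the plan says.** The non-inferiority label appears on the title page and in Sections 6.1, 6.2 and 6.4.4; for example, "This non-inferiority study used a prospective, longitudinal, randomized design with repeated measures". Aim 2 (Section 5) is to demonstrate that kiosk UVB "is at least equivalent to D3 oral intake to raise or maintain serum 25(OH)D levels over a 10-week intervention period". Section 6.2 adds that "it is important to evaluate its equivalence to standard of care", and Section 6.5.3 states that "Serum 25(OH)D level is the primary endpoint used to establish whether the treatment in the phototherapy kiosk group is equivalent".

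The direction of the comparison is given only as an expectation in Section 6.5.3: "the serum 25(OH)D levels will be equal to, or not less than, that of the oral supplementation group". It carries no number.

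The one sentence on group comparison is in Section 6.1: "we will analyze data using repeated measures analysis of variance adjusting for significant covariates such as 25(OH)D level at baseline". Logistic regression (Sections 6.1 and 6.4.7) is for prediction and for relationships among variables. Section 6.6.1 describes exploratory analyses, a normality test and medians with IQRs, but no test between groups. Section 6.6.2 gives 60 required, 30% dropout, and a minimum of 78 with 120 requested. It gives no margin, SD, alpha or power.

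On timing, week 10 is implied as primary: Aim 2 covers 10 weeks, and at 14 weeks "25(OH)D is drawn to document sustainment of treatment effect". No section names it as the primary analysis time point.

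**The concern.** A non-inferiority conclusion needs a margin and a rule, usually that the confidence limit on the unfavourable side must exclude a deficit of that size. The usual group test in a repeated-measures ANOVA has a null of no difference. Rejecting it in the wrong direction shows inferiority. Failing to reject it shows nothing about equivalence. A reader who follows the plan can therefore fit the model but cannot say whether Aim 2 was met.

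The documents do not say that a non-significant result will be read as equivalence, but nothing rules it out. If it were read that way, a smaller or noisier trial would be more likely to succeed. Because no time point is named, the group effect could also average week 10 with the off-treatment week-14 draw. If the difference between groups shrinks after treatment ends, that would dilute a week-10 deficit.

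**Working it through.** **The plan's own figures.** The required 60 cannot be reproduced, because margin, effect size, SD, alpha and power are all absent. The 78 is 60 × 1.3. Dividing by 0.7 would give 86, and 78 × 0.7 leaves about 55. The requested 120 leaves 120 × 0.7 = 84.

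**Inputs for illustration.** From the documents: 60 required, 120 requested, 30% loss, and "Serum 25(OH)D has a circulating half-life of 15 days" (Section 6.5.1). Assumed, because the documents give none: SD 10 ng/mL (range 7 to 12), correlation ρ = 0.6 of baseline with each follow-up, true week-10 kiosk deficit 4 ng/mL, illustrative margin 4 ng/mL, 1:1 allocation, normal data, two-sided 5%. So n = 30 or 42 per arm, with 2n − 3 degrees of freedom and the non-central t distribution.

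**(a) Chance that a real week-10 deficit is non-significant.** This is a single-time-point ANCOVA approximation, not the planned test.
- Residual SD: s = SD × √(1 − ρ²) = 10 × √0.64 = 8.0.
- Standard error: s × √(2/n) = 2.07 (n = 30) or 1.75 (n = 42).
- Non-centrality: 4/2.07 = 1.94 or 4/1.75 = 2.29; critical t is 2.00 or 1.99.

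| SD | 60 completers | 84 completers |
|---|---|---|
| 7 | 22% | 10% |
| 10 | 52% | 38% |
| 12 | 65% | 53% |

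**(b) The same for a group effect averaging weeks 10 and 14.** With correlation r between the two draws, s² = SD² × ((1 + r)/2 − ρ²). At SD 10 this gives s = 7.0 for r = 0.7 and 7.7 for r = 0.9. The effect is the mean of the two deficits. Ranges below are for r = 0.7 to 0.9.

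| Week-14 deficit | Mean deficit | 60 completers | 84 completers |
|---|---|---|---|
| 4 (persists) | 4.0 | 41–49% | 27–35% |
| 2 (halves) | 3.0 | 63–68% | 51–58% |
| 1.1 (15-day half-life) | 2.55 | 72–76% | 62–68% |

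The last row uses 4 × 0.5^(28/15) = 4 × 0.274 = 1.1. Averaging helps if the deficit persists and hurts if it fades.

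**(c) Power if the claim is kept.** Success means that the lower limit of the two-sided 95% CI for the week-10 difference lies above −4, with no true difference.

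| SD | 60 completers | 84 completers | Completers for 80% power |
|---|---|---|---|
| 7 | 78% | 90% | 64 |
| 10 | 48% | 62% | 128 |
| 12 | 35% | 47% | 184 |

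At SD 10, a 3 ng/mL margin gives 30% and 40%; a 5 ng/mL margin gives 66% and 81%. Under such a rule, the chance of a wrong claim when the true deficit equals the margin is 2.5%.

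**The case against.** The strongest reply is that this is a pilot feasibility study, sized as one, with serum analyses that Section 6.6.1 calls exploratory. Aim 1 is untouched and the remedy is mainly wording. That limits the harm but does not remove the gap: Aim 2 is to demonstrate, and Section 6.5.3 is to establish, a conclusion that the plan gives no means of reaching.

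A second reply is that fuller statistical text may exist. Section 6.6.1 refers to an original analysis plan. MCAR is defined in the abbreviations, and references 23 to 25 (effect sizes, a missing-data test, outlier labelling) are not cited in the text supplied. This is fair, and the finding is limited to these documents. It does not show that a margin was set.

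Third, the dilution argument is conditional. It requires the difference to shrink after treatment. Section 6.5.1 also says that serum levels do not reflect tissue stores, so decay of the group difference at the circulating half-life is not established. It also assumes that the repeated levels are weeks 10 and 14; if baseline is a level too, the group-by-time term would be the natural test, and calculation (b) would not describe it. These points stand as limits on (b).

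Finally, the numbers rest on assumed inputs. The analysed number could exceed 84, since one follow-up draw suffices, or fall to about 55 if only 78 enrol. The omission itself depends on none of these figures.

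**Conclusion.** The concern holds and must be fixed. On the supplied documents, the primary endpoint carries a non-inferiority claim with no margin, alpha or decision rule, and the named analysis cannot reach that claim as written. The analysis model is sound; what is missing is the contrast, the time point and the rule.

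Under the assumed central values (SD 10, correlation 0.6, deficit or margin 4 ng/mL), reading week-10 non-significance as equivalence would miss a real deficit in roughly four to five trials in ten. Keeping the claim at that margin would need 128 completers for 80% power, more than the 120 to be enrolled. Both results move widely with SD. Confidence in the omission is high; the sizes are illustrations only.

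**What to change.** 1. Check whether the original analysis plan mentioned in Section 6.6.1 fixed a margin and rule before data were seen. If so, state them in the plan.
2. If it did not, and outcome data have been seen (the title page lists completion on 11 March 2019) or no margin can be justified, remove non-inferior and equivalent from the efficacy conclusions. Report the baseline-adjusted kiosk-minus-supplement difference in 25(OH)D at the 10-week draw, as the week-10 contrast from the planned model, with its two-sided 95% CI, as a pilot estimate.
3. Only if outcomes are still unseen, fix a margin in ng/mL in advance, justified against the supplement's expected effect relative to no treatment. Claim non-inferiority only if the lower 95% limit lies above minus that margin.
4. In every case, name week 10 as the primary time point, keep week 14 for sustainment, and state that a non-significant ANOVA will not be read as equivalence. Table 1 places the blood test and the last exposure both at Time 6 without giving their order, so state what the week-10 sample represents.

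The fallback in step 2 is wording only; its price is a weaker claim. Step 3 has a real power cost, shown in calculation (c), and a smaller margin or larger SD makes it worse.
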